8.2.2 Case Number of each diseases in clinical trial and their determination reasons

There is strict restriction for inclusion and exclusion standards for recruited patients in the trial protocol, it can be considered that the current research is carried out with the target of patients with individual indications, and the 108 cases mentioned above all belong to the same disease category, not necessary for further division.

8.2.3 The minimum and maximum subject number in each clinical trial institution and their reasons

The current research shall be carried out in multiple clinical research institutions at the same time, in principle, it shall be evenly distributed into the various center grouping as much as possible, to ensure the sufficient center representativeness. However taking into consideration of the feasibility and inclusion schedule, it would carry out adjustment for the inclusion number in all the participated unit according to the actual conditions, to ensure the balance of inclusion scale for each center, while for a specific center, the final inclusion scale shall be no more than 50% of the total cases number.

8.3 Significance level and Test Power for Clinical Trial

In the current trial, the significance level for the statistical test shall take 5%(on both sides)(unless specified otherwise), and the test power take 80%.

8.4 Expected Falling Off Rate

In the sample volume design procedures, it is expected that the maximum possible falling off rate during research period shall be 10%, which include all the conditions that cannot be included into final major analysis, it is generally referred to severe breach against the research

protocol (influencing the major efficacy evaluation) judged by the major researchers. The including conditions are: The patients do not comply with the inclusion criteria; the patients fail to use any research related products; the patients use the third party products during research; the patients fail to complete follow up according to prescription; or it is accompanied by treatment influencing efficacy, etc. All of the conditions mentioned above shall be counted into the overall falling off rate.

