7.1.5.3. Standards and Procedures for the stop of trial/test treatment

Falling off standard:

All the subjects filling out the informed consent and qualified in screening for enrollment into randomized research, when they withdraw from the trial research in any time for any reasons, so long as they failed to accomplish the observation cycle prescribed by the protocol, they shall be deemed as falling off cases, and stop the trial. Common falling off causes include:

- (1) Occurrence of serious adverse events resulted in the furthering completion of the trial;
- (2) Changes in diseases conditions, unsuitable for furthering completion of the trial;
- (3) Loss of follow up;
- (4) The patients or their family members demanding withdrawal from the trial;
- (5) Incapable of furthering completion of the trial for any other reasons;
- (6) The subjects are poor in compliance, influencing the efficacy and safety judgment.

After the subjects' falling off, the researcher must contact the subjects for all possibilities, and ask for the reasons and accomplish all the assessment items possible of completion. When the patients withdraw due to the allergic reaction, adverse reactions, and invalid treatment, the researchers must adopt the corresponding treatment measures according to the actual conditions of the subjects.

Rejecting Criteria:

All the cases already included however comply with any of the following conditions, must be rejected:

- (1) Misdiagnosis (without application of any testing instrument);
- (2) Patients without any testing records (without application of testing instrument);
- (3) Patients incompliance with the inclusion/exclusion criteria (without application of testing instrument);
- (4) Due to the application of any forbidden drug, which results in the incapability for effective evaluation (without application of testing instrument).

For rejection cases it must be explained for the reasons, and their CRF Table must be preserved and ready for review. Without treatment statistical analysis, however after receiving

treatment, with at least one effectiveness and safety records, the patients can participate in the safety analysis according to conditions.

Standards/Procedures for the stop of trial/test treatment:

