8.1.2 Statistical Analysis Method

- (1) Description analysis: The counting data were described with frequency number and composing rate; and the measurement data applied mean value, standard deviation,

maximum value, minimum value, as well as the median value, 25 and 75 percentiles.

- (2) Baseline demographic statistical analysis: On the basis of descriptive analysis, between the counting data groups, it applies continuous calibration χ^2 inspection, when the unit block theoretical frequency number over 25% is lower than 5, it applies the Fisher's Exact Test; for normal distribution, the comparison between different counting data groups, it applies grouping t Test; for abnormal distribution, it applies Wilcoxon Rank and Wilcoxon Rank Sum Inspection for comparison between groups.
- (3) Efficacy Analysis: For occlusion successful rate 6 months after implanting as the primary efficacy indices, it applies the adjustment of central effect with CMH Chi-square test as the method to compare between different groups, apart from the assessment for the successful rate between trial and control groups, it should also be assessed for the difference value between successful rate in different groups as well as 95% confidence interval. For other efficacy indices, the comparison method between groups is similar as the baseline analysis. For within group counting data comparison with normal distribution, it applies matched t Test; for within group counting data comparison with abnormal distribution, it applies Wilcoxon Sign Rank Test.
- (4) Safety Evaluation: Describe the case number of normal before treatment and abnormal after treatment and their percentage respectively according to the test group and control group. Described the adverse events with the case number of adverse events and their occurrence, and carried out continuous calibration χ^2 test or Fisher precision probability method test. At the same time, it shall be described in details of the embodiment for all adverse events, their degrees and relevance with the research products.
- (5) For primary efficacy indices, the statistical analysis shall be carried out under the significance level with 0.025 on single side (which correspond to 95% confidence interval on one side confidence limit), for other indices, all the statistical analysis

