8.2 Sample Volume Calculation

8.2.1 Total Sample Volume

It is expected of 108 cases of patients included in the trial, randomized into the trial group or control group with the ratio of 1:1, with 54 cases in each group. The calculation of sample volume is based on the primary evaluation indices, namely the 6 months occlusion successful rate after implanting.

In combination of the current clinical evidence and experience assessment by the clinical experts, it is assumed that the 6 months occlusion successful rate is about 98% after implanting in patients of the control group, it is expected the trial products in the trial group in application can also reach the same successful rate level, it is determined by clinician and sponsor after joint discussion that the non-inferiority limit value is set as 8%, when the significance level for statistical test takes 2.5% on single side, with test power of 80%, taking into account of the maximum incidence of 10% falling off rate and randomized block length in the research, according to statistical principles, it is calculated that, for each group, it is necessary for 54 cases of patients inclusion, total case number in both groups are 108 cases.

The corresponding sample volume calculation equation is:

$$n = \frac{\left[\mu_{1-\alpha} \sqrt{2\bar{p}(1-\bar{p})} + \mu_{1-\beta} \sqrt{p_T(1-p_T) + p_C(1-p_C)} \right]^2}{(\Delta - (p_T - p_C))^2}$$

In the equation p_T correspond to the 6 months occlusion successful rate after implanting in trial group, and p_C represents 6 months occlusion successful rate after implanting in control group; $\bar{p} = (p_T + p_C)/2$ is average successful rate between both groups; Δ corresponds to non-inferiority limit value; μ represents the percentile of standard normal distribution, α corresponds to Type I error level for statistical test, which is 0.025 here, while β corresponds to Type II error level for test, when calculated, it takes 0.2 (corresponding to 80% of test power).

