8.9 Selection Standard and Causes for subjects included into the analysis

Statistical analysis shall be based on the foundation of the following analysis population, before the initiation of statistical analysis, it would make clear definition for the analysis population, which include:

Full Analysis Set (FAS): The subject set defined according to the Intention To Treat Principle, referred to the data set of all the subjects participated in randomization and applying research devices. For patients fail to observe of the primary efficacy indices, it is planned to apply WCCF (Worst Case Carry Forward) strategy to carry out cutting and transfer for the missing data.

Per-protocol population set (PPS): Refer to all the treatment population subgroup finished the trial and excluded the severe breach of protocol (refer to research subject breaching the inclusion criteria or in compliance with the exclusion criteria, etc).

The primary efficacy indices analysis shall be carried out on the basis of Full Analysis Set and Per-protocol population set at the same time; in addition, all the baseline demographic data and secondary efficacy analysis shall be carried out on the basis of Full Analysis Set, and the safety evaluation shall also be carried out on the basis of Full Analysis Set (Therefore, it would not define SS separately).

8.10 During validation of hypothesis, it is excluded of specific information and their causes (if applicable)

Not applicable.

9. Data Management

It applies Electronic Data Capture(EDC) to complete the collection of trial data.EDC system has undergone strict testing, completely meet the requirements of “Quality Management Norm for Clinical Trial of Medical Devices”, “Data Management Work Technique Guideline for Clinical Trial”.Before the online of the system, it is necessary to carry out training and testing for the relevant application staff, to ensure that the system meet the requirement of the trial.After formal online, relevant staff would obtain the account and password.The account binds the roles and authority of the clients, and they should properly preserve the account information, and forbidden to divulge the account information to any others, or replace others in their performance of others rights.

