the occluder selected is too large, due to the small defect opening, the waist extension of the occluder is limited, and the edge is relatively long, or the disk of the occluder forms a spherical appearance, which occupies a larger space after release and affects tricuspid valve closure. Echocardiography monitoring shall be performed during the operation. If obvious tricuspid regurgitation is found, occlusion treatment shall be abandoned.

5) Aortic regurgitation

It is related to occluder and operation. For example, for VSD with poor edge, the edge of the occluder selected which is larger than the distance from VSD to aortic valve, and direct contact of the edge of the occluder with aortic valve will affect the closure of aortic valve.

The disc diameter of the left ventricle of the occluder is larger than 50% of the circumferential diameter of the outflow tract of the aortic valve, and after the occluder is placed, the outflow tract of the left ventricle can be deformed, resulting in incomplete closure of the aortic valve.

6) Residual shunt

Shunt through the occluder disappears in a short period of time after the polyester membrane mesh hole in the occluder is filled with blood components. Obvious residual shunt is found in patients treated by porous VSD occlusion because the occluder fails to completely cover the inlet and outlet. For porous VSD, the left of the occluder shall be ensured to completely cover the defect inlet, otherwise, the occlusion treatment shall be abandoned.

7) Hemolysis

It is related to the existence of residual shunt. High-speed blood flowing through the occluder can cause hemolysis, which is manifested as soy sauce urine, chills, anemia, renal insufficiency, etc. In this case, close observation shall be made. For patients with mild hemolysis, aspirin shall be stopped, hemostatic drugs shall be given intravenously, and sodium bicarbonate shall be given orally or intravenously. In case of shunt complicated with hemolysis caused by spring coil, another occluder or spring coil can also be placed. If hemoglobin < 70g/L, the occluder shall be removed surgically.

8) Acute myocardial infarction

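### The exclusion wording in 8.4 and 8.9 lets patients whose study occluder failed leave the per-protocol set, which biases that co-primary analysis toward non-inferiority

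*Combined protocol and SAP*

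**What the plan says.** - **8.4 Expected Falling Off Rate.** The 10% allowance covers every condition that keeps a patient out of the main final analysis, described generally as severe breach affecting the efficacy evaluation. The list includes: "the patients use the third party products during research; the patients fail to complete follow up according to prescription; or it is accompanied by treatment" that influences efficacy. Nothing exempts treatment given because the study occluder failed.
- **8.9, PPS definition.** "Refer to all the treatment population subgroup finished the trial and excluded the severe breach of protocol". The examples are eligibility breaches, and the list is left open. The primary endpoint is analysed on FAS and PPS together.
- **8.9, FAS definition.** All randomised patients in whom a device was applied. An unobserved primary outcome is imputed by worst case carried forward (WCCF).
- **8.7.** Data from patients who withdraw or are terminated early go into the final analysis, with imputation.
- **7.1.5.3.** Any patient who does not complete the observation period is a falling-off case. Listed causes include serious adverse events and a changed disease condition. Ineffective treatment is foreseen as a reason for leaving: "When the patients withdraw due to the allergic reaction, adverse reactions, and invalid treatment". That sentence sets a duty of care and is not itself an exclusion rule.
- **13.4.** A shed occluder leads to removal and surgical repair of the defect, and surgical removal is also foreseen in haemolysis.
- **7.1.6.** Success is defined by the 6-month echo alone. Re-intervention is not mentioned.
- **8.5.** The lower 95% limit must exceed -8%. No analysis set is named.

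**The concern.** For an implanted occluder, removal, repair, added treatment and withdrawal for an adverse event can all be results of the assigned device. If such patients leave the PPS, the arm with more failures loses more of them and the difference moves toward zero. In a non-inferiority trial the PPS is run partly to guard against dilution of a true difference. Here it could become the more lenient of the two primary sets.

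The question is which events justify exclusion. Who judges the exclusions, and how missing echoes are imputed, are separate matters.

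**Working it through.** **Inputs.** One-sided level: "the statistical analysis shall be carried out under the significance level with 0.025 on single side" (8.1.2). Control rate: "it is assumed that the 6 months occlusion successful rate is about 98% after implanting in patients of the control group" (8.2.1). Trial arm: "it is expected the trial products in the trial group in application can also reach the same successful rate level" (8.2.1). Margin 8 points, power 80%, 1:1 allocation, 10% falling off (8.2.1).

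**Plan's own figure.** The formula in 8.2.1 gives n = (1.960 + 0.842)² × 2 × 0.98 × 0.02 / 0.08² = 48.07. Then 48.07 / 0.9 = 53.4, so 54 per group. The stated size reproduces and is not at issue.

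**Effect on the PPS.** Take 54 per arm with true success of 90% (trial) and 98% (control), a difference of exactly -8 points, so that non-inferiority is false. Let q be the share of failures in each arm that leave the PPS. The documents give no value for q, so a range is shown. Expected PPS success is p / [p + (1 - p)(1 - q)].

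For q = 50%: 0.90 / 0.95 = 94.74% and 0.98 / 0.99 = 98.99%, a difference of -4.25 points.

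The chance that the lower 95% limit exceeds -8% comes from exact binomial enumeration. The plan names no interval method, so Wald and Newcombe are both shown. In the last column the FAS scores dropped patients as failures and both sets must pass.

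| q | PPS difference (points) | False NI, PPS alone: Wald / Newcombe | False NI, both must pass: Wald / Newcombe |
|---|---|---|---|
| 0% | -8.0 | 4.4% / 1.5% | 4.4% / 1.5% |
| 25% | -6.2 | 10.9% / 3.2% | 4.0% / 1.2% |
| 50% | -4.2 | 26.5% / 8.2% | 4.1% / 1.1% |
| 75% | -2.2 | 61% / 26% | 4.3% / 1.2% |

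**If rescue counts as success in the FAS.** Suppose instead that the dropped patients have a clean 6-month echo and are scored as FAS successes under 7.1.6. Requiring both sets then gives 10.9%, 26.5% and 61% (Wald) or 3.2%, 8.2% and 26% (Newcombe). The FAS protection is gone.

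**Would it be noticed?** Expected exclusions are 54 × (0.10 + 0.02) × q = 6.48q, or 1.6, 3.2 and 4.9 patients. These are 1.5%, 3.0% and 4.5% of 108, well inside the planned 10%.

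**Illustration.** With 6 trial and 1 control failures, all kept, 48/54 v 53/54 is -9.3 points, with lower limits of -18.4 (Wald) and -20.4 (Newcombe). Both fail. With all seven removed, 48/48 v 53/53 is 0 points and the Newcombe lower limit is -7.4, a pass. With only three of the six trial failures removed, 48/51 v 53/54 is -4.0 points and still fails (Wald -11.4, Newcombe -14.2).

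**The case against.** The strongest reply is that the FAS already protects the conclusion. It keeps every randomised patient in whom a device was applied, imputes a missing outcome by WCCF, and is analysed together with the PPS, while 8.7 keeps withdrawn patients in. If both sets must pass and dropped patients are FAS failures, the error rate does not rise. This stands. It depends, however, on a both-sets rule that 8.5 does not state. WCCF also acts only when the outcome is unobserved, so it does not reach a rescued patient with a clean echo.

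A second reply is that 8.4 is a planning allowance, whereas 8.9 defines the PPS and gives only eligibility breaches as examples. A rescued patient who attends the 6-month echo has arguably finished the trial, and third-party products might mean another maker's device used at the outset. This also stands in part: that rescued patients leave the PPS is an inference from the shared term severe breach and the open-ended list, and is not an express rule. The finishers-only condition, however, removes early withdrawals without any inference, and added treatment that influences efficacy is wide enough to cover rescue.

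**Conclusion.** The concern holds as a defect in the PPS definition, with a known direction of bias. The wording allows device failures to leave one of two primary sets, and 8.4 and 8.7 contradict each other on withdrawn patients. On the PPS alone, false non-inferiority rises from 4.4% to about 11%, 27% or 61% (Wald), or from about 1.5% to 3%, 8% or 26% (Newcombe), if a quarter, a half or three quarters of failures are dropped. These figures rest on the assumed dropped share, equal in both arms, and on true rates of 90% v 98%.

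Two stronger readings go beyond the documents. A reader might take these figures as the trial's overall error rate. That would need the PPS to decide alone or rescued patients to count as FAS successes; the documents leave both open and prescribe neither. A reader might also infer that the PPS would show no difference between arms. That follows only if nearly all failures are removed; with half removed, about -4.2 of the -8 points remain.

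**What to change.** Make these changes before database lock:

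1. In 8.4 and 8.9, limit PPS exclusions to deviations that are not consequences of the assigned device, such as an eligibility breach present before implant, or no study device used.
2. In 7.1.6 and 8.9, state that patients whose study occluder was removed, replaced or supplemented, or who withdrew for a device-related event or ineffective occlusion, count as failures in their randomised arm in both FAS and PPS. Report their number by arm.
3. In 8.5, state that both FAS and PPS must meet the -8% margin.
4. Reconcile 8.4 with 8.7 on withdrawn patients.

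The cost is wording only, with no new patients or data and no change to clinical management. Section 8.8 says analysis sets are in principle not altered when the analysis plan is revised, so the change should be made openly and recorded. The downside is that success rates become slightly less favourable.

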8.5 Eligible/Ineligible Criteria of Clinical Trial Results

From statistical angle, it is judged of the eligibility and ineligibility of the trial results, correspond to the validation for initial hypothesis inspection. For the current research, the primary evaluation index is the 6 months occlusion successful rate after implanting, and the comparison type of the trial is non-inferiority inspection, which is planned to be proved through trial result. Compare the trial group and control group product, they both have the same treatment efficacy.

In conclusion, the judgment of trial results shall be based on the difference between the occlusion successful rates in the trial group and the control group, if the results demonstrate: The occlusion successful rate in trial group subtracting that in control group in the lower limit of 95% confidence interval is greater than -8% (the non-inferiority limit value setup in advance), it can be explained as non-inferiority conclusion is established. Otherwise, the non-inferiority conclusion can not be reached.

8.6 Standard and Reasons for termination of trial based on the statistical

The current trial has no pre-set up middle term analysis and early termination standard correspondingly, therefore, it is inapplicable here. All the statistical analysis shall be carried out after the completion of data gathering, cleaning and final lock up.

8.7 Data statistical method, in combination with missing, unused or wrong data (including withdrawal and termination mid term) as well as the processing method for unreasonable data.

Statistical analysis procedures are implemented strictly according to the Standard Operation Procedure (SOP) by the medical statistical department of National Cardiovascular Disease Center. For details, please refer to relevant documents.

For missing data that may occur during research procedures, during analysis, it shall carry out cutting and transfer targeting at the missing of primary efficacy indices, for the cutting and

transfer method in details, it shall be explained in the prospectus for statistical analysis. In general, it applies single value cutting and transfer method such as LOCF (Last Observation Carry Forward) strategy or WCCF (Worst Case Carry Forward) strategy to carry out processing for the missing data in the primary indices. For the occurrence of missin data in other indices, it would not carry out cutting and transfer, instead it is carried out of analysis for data actually observed.

Wrong and unreasonable data shall be screened during the data screening procedures before statistical analysis. For mid term withdrawn or terminated of the trial, the data of this part of patients shall be included into the final statistical analysis. In the statistical report, it would carry out in detail explanation for the causes of withdrawal or termination patients, for missing data resulted from early stage withdrawal, it should be cutting and transferred according to the missing data processing strategy mentioned above.

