7.1.6. Effective Evaluation Method

I. Effective parameter explanation

Primary Efficacy Indices: 6 months occlusion success rate.

6 months occlusion success (definition): 6 months occlusion success refer to ultrasonic cardiogram inspection in follow up 6 months after operation, there is no residual shunts in the occlusion location or only with minor amount of residual shunts.

Secondary Efficacy Indices: Surgical Technical Successful Rate.

Surgical Technical Successful Rate (Definition): Surgical intervention delivery devices through the occluder (trial group) or occluder intervention delivery devices (control group) implanting the occluder and then safely released.

Secondary Efficacy Indices: Technical Successful Rate.

Technical Successful Rate (Definition): Surgical intervention delivery devices through the occluder (trial group) or occluder intervention delivery devices (control group) implanting the occluder and then safely released, without occluder shedding during operation.

II. Evaluation, recording and analysis of effective parameter method and time selection

Immediate, 1 month, 3 months, 6 months occlusion success after intervention occlusion operation, namely ultrasonic cardiogram suggesting the residual shunt bunch diameter no higher than 2mm, according to the Doppler shunts signal from left to right judgment, it is better in effect to have no shunts signal from left to right; with diameter lower than 1mm from left to right shunts signal as trace amount of residual shunts; with diameter between 1 and 2mm as minor amount of residual shunts.

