8.8 Reporting Procedures Deviated from the original statistical plan

The statistical analysis prospectus is in need of the confirmation by the sponsor and the major researcher, and finalize before the database lock up. Before finalize, it can be modified of the initial analysis prospectus targeting at the actual conditions in the trial procedure, in principle, it would not modify the major analysis principles, methods and analysis set, and all the modification shall be recorded.

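### Section 8.7 allows LOCF or WCCF for missing 6-month outcomes, 8.9 names only an undefined WCCF, and carrying clean early echoes forward can score a failed occluder as a success

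*Combined protocol and SAP*

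**What the plan says.** Section 7.1.6 sets the primary endpoint at month 6: "6 months occlusion success refer to ultrasonic cardiogram inspection in follow up 6 months after operation", with no residual shunt or only a minor one. The same section reads occlusion success at earlier visits too ("Immediate, 1 month, 3 months, 6 months occlusion success after intervention occlusion operation"), all against one 2 mm criterion.

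Section 8.7 imputes missing primary-endpoint data, in general by a single-value method "such as LOCF (Last Observation Carry Forward) strategy or WCCF (Worst Case Carry Forward) strategy". On the detail of the method it says "it shall be explained in the prospectus for statistical analysis". Withdrawals follow the same route: "for missing data resulted from early stage withdrawal, it should be cutting and transferred according to the missing data processing strategy mentioned above".

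Section 8.9 is narrower. For FAS subjects whose primary outcome is not observed, "it is planned to apply WCCF (Worst Case Carry Forward) strategy to carry out cutting and transfer for the missing data". Neither section says what WCCF assigns to a subject whose observed echoes were all clean.

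Section 7.1.5.3 lists reasons for leaving. The first is "Occurrence of serious adverse events resulted in the furthering completion of the trial", and a change in disease condition is the second. Section 8.8 requires the analysis prospectus to be final before database lock. Until then, "it can be modified of the initial analysis prospectus targeting at the actual conditions in the trial procedure".

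**The concern.** An early echo judged on the month-6 criterion can be carried straight into the month-6 endpoint. A subject with a clean immediate echo who leaves in week 2 is then a 6-month success under LOCF. The result is the same under WCCF if it means the worst value observed, because there is no bad value to carry.

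This matters because leaving can be related to the outcome. Section 13.4 foresees displacement, detachment, and hemolysis leading to surgical removal. No section says that a subject with such an event is scored as a failure. Section 7.1.5.5 expects residual shunts mainly in the first 3 months, so a last echo taken immediately after surgery or at month 1 is the weakest basis for a month-6 value.

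If such failures fall more heavily on the test arm, carrying clean echoes forward hides them and favours the non-inferiority claim. The wording also leaves a choice of rule, or of the meaning of WCCF, to a document that need only be final before lock.

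**Working it through.** **Inputs.** Section 8.2.1: 98% success in both arms, margin 8 points, one-sided alpha 0.025, power 80%, at most 10% falling off, 54 per arm. Section 8.5: non-inferiority if the lower 95% limit of test minus control exceeds -8%. The interval method is not stated, so an unstratified Wald interval is assumed, with Newcombe as the alternative.

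**1. The plan's sample size.** With equal rates its formula reduces to n = (1.960 + 0.842)² × 2 × 0.98 × 0.02 / 0.08² = 48.07 per arm. Then 48.07 / 0.90 = 53.4, giving 54, as stated. Dividing by 0.90 allows for leavers who drop out of the analysis. It does not allow for leavers who stay in it as failures.

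**2. Same data, two rules (illustration).** Suppose 5 of 54 per arm leave after clean echoes and 48 of 49 completers per arm succeed.

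- Carried forward: 53/54 v 53/54. SE = √(2 × 0.9815 × 0.0185 / 54) = 0.0259, so the lower limit is 0 - 1.96 × 0.0259 = **-5.1%**: met.
- Scored as failures: 48/54 v 48/54. SE = √(2 × 0.8889 × 0.1111 / 54) = 0.0605, lower limit **-11.9%**: not met.
- One leaver, in the test arm only: 53/54 v 53/54 becomes 52/54 v 53/54, and the limit goes from -5.1% to -8.04%: not met.

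Under Newcombe the first two limits are -8.1% and -12.6%, so neither meets the margin. The reversal in this example therefore depends on the interval method.

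**3. False claims.** True rates of 90% (test) v 98% (control) lie exactly on the margin. Exact binomial enumeration, 54 per arm:

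| Situation | Analysed rates | Wald | Newcombe |
|---|---|---|---|
| No missing data | 0.90 v 0.98 | 4.4% | 1.5% |
| 10% missing at random, carried forward as success | 0.9×0.90+0.1 = 0.91 v 0.9×0.98+0.1 = 0.982 | 6.3% | 2.1% |
| 10% missing at random, scored as failure | 0.9×0.90 = 0.81 v 0.9×0.98 = 0.882 | 3.5% | 3.3% |
| 10% of test arm leave with clean echoes, 25% of them truly failed, carried forward | 0.90+0.1×0.25 = 0.925 v 0.98 | 13% | 5% |
| As above, 50% truly failed | 0.90+0.1×0.50 = 0.95 v 0.98 | 32% | 14% |

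The 25% and 50% shares are assumptions, with the control rate held at 98%.

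The third row shows why equal failure coding is not always conservative. It shrinks the true 8-point gap to 0.882 - 0.81 = 7.2 points, and the Newcombe rate rises from 1.5% to 3.3%.

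**4. Cost in power.** True success 98% in both arms, share m missing. Carry-forward gives 0.98(1-m) + m per arm; failure coding gives 0.98(1-m).

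| Missing | Carried forward, Wald / Newcombe | Failure, Wald / Newcombe |
|---|---|---|
| 0% | 77% / 46% | 77% / 46% |
| 5% | 78% / 47% | 40% / 31% |
| 10% | 79% / 48% | 26% / 23% |

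**The case against.** **The two sections need not conflict.** A reader might infer a flat contradiction. The text does not go that far: 8.7 is general and defers detail, 8.9 is specific, and WCCF is one of the options that 8.7 allows. Section 8.9 can be read as narrowing 8.7. This stands. What remains is an option left open and a term left undefined.

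**WCCF may already mean failure.** For a binary endpoint, worst case can mean the worst possible outcome. On that reading 8.9 already contains the safe rule and only LOCF in 8.7 is wrong. The documents do not settle the meaning.

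**Exit assessments.** Section 7.1.5.3 tells the researcher to contact leavers and complete whatever assessments are possible. A failed exit echo would be both the last and the worst value, hence a failure under every rule. This stands, so the misclassification needs a failure that no echo captured.

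**Limits on late change.** A reader might infer a free choice of rule once results by arm are known. Section 8.8 says that the main principles, methods and analysis sets will in principle not be changed and that changes are recorded. Section 8.7 puts analysis after lock. The safeguard is real but soft, and settling a point left open is arguably not a change. Open-label conduct is only an inference: no masking of operators or echo readers is described, but the documents do not call the trial open label.

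**The PPS.** The primary endpoint is also analysed in the PPS, which is limited to subjects who finished. That mostly avoids imputation, but it drops the leavers and so cannot show their failures. Section 8.9 does not say that both sets must pass.

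**The size of the swing.** At 10% missing the rules differ by 79% - 26% = 53 points from the rounded Wald figures (48% - 23% = 25, Newcombe). A reader might take this for false claims. It is not: both arms truly succeed at 98%, so every claim counted is correct, and the gap is almost all power lost under failure coding.

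**Conclusion.** The point holds as a defect in a stated rule. Section 8.7 permits LOCF for the primary endpoint and applies its strategy to early withdrawals. LOCF, or WCCF read as the worst observed echo, can count a subject whose occluder failed after a clean echo as a 6-month success. Nothing in the documents scores known device failure, removal or re-intervention as failure.

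The effect on false claims is modest when data are missing at random: 4.4% to 6.3% (Wald) at the plan's maximum of 10%. It becomes serious only if leaving is tied to device failure in the test arm, and no document says how often that would happen. The 13% and 32% figures show what would follow from assumed shares; they are not forecasts. All figures rest on 54 per arm and an interval method that the plan leaves open.

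The documents do not show that the sponsor will use LOCF, that WCCF will be read as the worst observed value, or that the choice will be made with knowledge of results by arm. They leave all three possible, which can be closed by wording.

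**What to change.** - Delete LOCF from 8.7.
- In 8.7 and 8.9, define WCCF in the same words: an FAS subject without a 6-month echo is a failure whatever earlier echoes showed, and so is any subject with known device failure, removal or re-intervention before month 6.
- Fix this rule before any data by arm are seen, and exempt it from modification under 8.8.
- Add one sensitivity analysis that scores missing test subjects as failures and missing control subjects as successes. It is a stress test, not a second gate: at 10% missing and 98% true success in both arms the expected difference is 0.882 - 0.982 = -10 points, already beyond the margin.
- Name the confidence interval method, since step 2 shows that it matters too.

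The cost in documents is wording in two sections, a line in 8.8 and one table. The cost in power is larger and must be stated. At 98% in both arms, the chance of meeting the margin falls from about 77% with no missing data to about 40% at 5% and 26% at 10% missing (Wald). The stated 80% is therefore approached only if few 6-month echoes are missing. The sponsor should recheck the sample size under the chosen rule and put effort into obtaining the 6-month echo, including from subjects who have left.
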